In this double-blind research study, 66 participants will be randomized to receive real or sham tDCS prior to receiving an established interactive upper limb (shoulder/elbow and wrist) robotic training regimen. During the lead-in period, each subject will attend 3 weekly visits to complete TMS screening and have outcome measures (see below) assessed. Following the lead-in period, each subject will attend 36 90-minute sessions (3 visits/week) over a 12-week period (or up to 14-weeks to allow for missed appointments) comprising the training period. These visits will include further TMS screening and outcome measures, TMS, tDCS and robot training. Subjects will undergo further outcomes measures upon discharge and during a final 6-month follow-up visit. All study procedures will be administered and supervised by a therapist. All visits will be conducted in either the robot and TMS suites at the Feinstein Institute for Medical Research or at the Burke Medical Research Institute (Fig. 1). Participants will additionally undergo five blood draws longitudinally during the study to determine if cytokine levels change over the course of rehabilitation intervention, and if those changes are correlated with improved functional outcomes and treatment group (sham vs. real tDCS).

Lead-in Period

- Week 1, Visit 1 (approximately 30 minutes)
 - TMS screening questionnaire
 - Outcome measures
- Week 2 & 3, Visit 2 & 3 (approximately 60 minutes each)
 - Outcome measures
 - One time 10cc DNA sample and 2 separate 4cc baseline blood draws (2 total draws)

Training Period

- Week 4-15, Visits 4-39 (approximately 90 minutes)
 - TDCS risk questionnaire (visit 4 only)
 - TMS
 - tDCS
 - Robotic training
 - 4cc blood draw at midpoint, session 18 (1 total)
- Weeks 16 Visit 40 (approximately 2.5 hours)
 - tDCS

[figure not shown]

Fig 1: Diagram of study design showing the relationship between the robotic training program with or without tDCS and the evaluation schedule

- Robotic training
- Outcomes measures
- 4cc discharge blood draw (1 total)

Final Visit

- Week 40, Visit 41 (approximately 60 minutes)
 - Outcome measures
 - 4cc follow up blood draw (1 total)

Clinical Outcome Measures

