The standard patient robot interaction involves visuomotor tasks, moving the robotic manipulandum according to targets on a computer screen mounted at eye level. The force required to move the robotic arm is minimal, comparable to moving unrestricted, and if a patient cannot move the robot arm, it will guide the limb to provide an adaptive sensorimotor experience. The robot program will always be tuned to the so-called progressive algorithm which blends the features of aiming or path trajectory correction and speed of movement.

Blood Sampling

As we are interested in assay of HMGB-1 and other cytokines longitudinally for the duration of the rehabilitation intervention, we will collect two baseline admission samples during admission evaluations 2 and 3. We will then collect additional samples at midpoint, treatment 18 (end of week 6), discharge, treatment 36 (end of week 12), and follow up, 6 months following the end of the rehabilitation intervention. Given the challenges of collecting samples within a specific 24 hour time period, the collection window will be extended such that all samples collected during the intervention will be obtained plus or minus one treatment day of the target (e.g. between treatments 17-19, 35-36-final evaluation day, respectively), and follow up samples will be collected plus or minus 7 days of the 6 month follow up target. Each of the 5 samples will be 4 cc each (green top tube). We will also obtain a one-time DNA sample, via the collection of a 10cc lavender tube (EDTA) at the time of the first sample collection. If this is not possible we will collect this sample at the time of a subsequent research blood sample collection. The total volume of blood drawn for each study subject will be no more than 30 cc over the duration of the study. All blood sampling will take place at the CRC during scheduled intervention and evaluation visits.

The blood will be centrifuged and prepared for HMGB-1 analysis by NS-LIJ Biorepository staff. If we miss sample collection across the eight time points the available collected samples from a subject will be analyzed. We will measure HMGB-1 and if the levels are elevated (>20ng/ml) we will return to the banked samples in the bio-repository to repository to assay samples for IL-1, IL-6, IL-8, IL-10, TNF and BDNF, all molecules known to be stimulated by HMGB-1 secretion [4, 5].

Randomization

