Previous studies indicate that stroke patients may differentially respond to non-invasive motor cortex stimulation protocols according to whether the lesion includes cortex, or is confined to white matter (52). Accordingly, we will use blocked stratified randomization to ensure our two comparison groups are balanced with respect to this known prognostic factor (cortical versus subcortical classification). Classification of this grouping will be assessed using CT or MRI with 'subcortical' defined as a stroke without involvement of cortical motor areas, and 'cortical' as infarction of cortical primary or secondary sensorimotor areas in addition to subcortical infarction.

Randomization of patients is performed by a statistician and epidemiologist, [name]. She will communicate the status to [name]. The switch is covered so that the therapist and the PI will not know the group assignment.

Blinding

The study is double-blind. All investigators interacting with patients will be unaware which patients are receiving real or sham stimulation. This includes the principal investigator and research fellows conducting robotic, neurophysiology or clinical assessments. The tDCS device has a coding option to program sham or real stimulation. [name], a histopathologist in [name] lab who is not involved with the robot project and has agreed to perform this toggling task will set the tDCS device for any particular patient. She knows [name] and we will establish communication between [name] – who will determine the randomization and [name] so that [name] and the Research Associate to be named will not have the patient's code. It is important to note that once the machine to deliver the transcranial direct current stimulation is toggled no further manipulation of the device is needed. The tDCSM operates automatically to deliver current or not. We will receive the coding option from the collaborating institution, and will reveal this information after analysis, unless there is a need to inform the PI in case of an adverse event. Patients will be asked at visit 9 and visit 15 (mid-point and end of the intervention period), whether they think they received real or sham stimulation.

Statistical Considerations and Data Analysis

Specific Aim 1 (Clinical): Determine if there is a statistically significant difference in the change in upper limb Fugl-Meyer and Wolf Motor Function score between subjects trained with and without tDCS prior to robotic training.

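### The two visit numbers set for the patient blinding question contradict their labels: visits 9 and 15 are training sessions 6 and 12 of 36, not the mid-point and end

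*Combined protocol and SAP*

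**What the plan says.** The Blinding section provides for two patient guesses of real or sham stimulation: "Patients will be asked at visit 9 and visit 15 (mid-point and end of the intervention period".

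The Visit Schedule sets the numbering. In the lead-in, "each subject will attend 3 weekly visits to complete TMS screening", which makes visits 1 to 3. After that, "each subject will attend 36 90-minute sessions (3 visits/week) over a 12-week period", with an allowance: "over a 12-week period (or up to 14-weeks to allow for missed appointments". The Training Period list gives "Week 4-15, Visits 4-39 (approximately 90 minutes", followed by the discharge visit, "Weeks 16 Visit 40 (approximately 2.5 hours".

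The plan also fixes its own mid-point and end. The Training Period list has "4cc blood draw at midpoint, session 18 (1 total". The Blood Sampling section has "additional samples at midpoint, treatment 18 (end of week 6), discharge, treatment 36 (end of week 12".

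The written visit list does not mention the blinding question. Fig. 1, the study diagram, is not shown in the available text.

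**The concern.** The sentence gives two instructions that cannot both be followed: ask at visits 9 and 15, and ask at the mid-point and the end. The schedule is organised by visit number, so a coordinator could reasonably ask at visits 9 and 15.

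The last guess would then come early in treatment. It would say nothing about whether patients had worked out their assignment by the time of discharge scoring. A guess not asked for at the time cannot be recovered later.

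The question is worth asking late because the arms may feel different: 20 minutes at 2 mA against a sham that ramps up and then falls to no current (tDCS Application section). Outcomes scored after training include the self-reported Stroke Impact Scale, where a patient's belief about assignment could matter. The documents do not show that blinding fails; this question is the plan's only test of it in patients.

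**Working it through.** **Inputs.** Three lead-in visits; training at visits 4 to 39 in study weeks 4 to 15; 36 sessions at three per week (all Visit Schedule). Mid-point at session 18 (Training Period list and Blood Sampling). End of the 12 weeks at treatment 36 (Blood Sampling).

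**Reproducing the plan's own count.** Visits 4 to 39 inclusive: 39 − 4 + 1 = 36. Three per week for 12 weeks: 3 × 12 = 36. The numbering is consistent with the stated 36 sessions.

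**Converting visits to sessions and weeks.** Session = visit − 3. Study week = 3 + (session ÷ 3, rounded up).

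| Visit | Session | Share of 36 | Study week |
|---|---|---|---|
| 9 (labelled mid-point) | 6 | 17% | 5 |
| 15 (labelled end) | 12 | 33% | 7 |
| 21 | 18 (plan's mid-point) | 50% | 9 |
| 39 | 36 (plan's end) | 100% | 15 |

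**Trying other readings.**

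- If visit meant session number: 9 ÷ 36 = 25% and 15 ÷ 36 = 42%. Neither label fits.
- If session 36 fell at visit 40, so that session = visit − 4: visits 9 and 15 are sessions 5 and 11. Neither label fits.
- If the numbers are study weeks: week 9 ends at session (9 − 3) × 3 = 18, and week 15 at session (15 − 3) × 3 = 36. Both labels fit exactly. This suggests that visit was written for week, but that is an inference.

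**Size of the gap if the visit numbers are followed.** Sessions after the last guess: 36 − 12 = 24, and 24 ÷ 36 = 67%. The visit 40 list also includes tDCS and robotic training. Counted as a 37th session, that gives 25 ÷ 37 = 68%.

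**Would changing visit to week be enough?** Training may run to 14 weeks. Assuming even spacing, which the documents do not give, the rate is 36 ÷ 14 = 2.57 sessions per week. Session 18 then falls at training week 7 (study week 10) and session 36 at training week 14 (study week 17). By the end of study week 9, 6 × 2.57 ≈ 15 sessions are done; by the end of study week 15, 12 × 2.57 ≈ 31. Fixed calendar weeks would come too early for both targets in such a patient.

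**The case against.** The strongest reply is that the intent can be recovered. The labels sit beside the numbers, the plan defines its mid-point and end elsewhere, and the match with study weeks points to a single wrong word. On that view the 67% is a worst case that arises only if staff ignore the labels.

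The consequence is also limited. No analysis in Statistical Considerations and Data Analysis uses the guesses. The wording leaves the blinding arrangements themselves unchanged. The primary Fugl-Meyer is performance-based and scored by blinded assessors. Even on the literal reading, two guesses per patient are collected. Fig. 1 might place the question, and reporting by arm goes beyond correcting a number.

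Much of this stands, and it limits the weight of the point: 67% is conditional, and no primary result is affected. It does not make the sentence right. The contradiction and the arithmetic are not in dispute, no written section reconciles them, and the cost of a wrong reading is permanent. The preference for sessions over weeks rests on the plan's own 14-week allowance; even spacing serves only as an illustration. Reporting by arm is an addition, but without it the guesses have no stated use.

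**Conclusion.** The concern holds. Visits 9 and 15 are sessions 6 and 12 of 36 on the plan's numbering, and neither is the mid-point (session 18, visit 21) or the end (session 36, visit 39).

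The effect depends on how staff read the sentence. Following the labels leaves no gap. Following the numbers leaves 24 of 36 sessions (67%) after the last guess, or 25 of 37 (68%) if the tDCS listed at visit 40 is delivered. The sample size and every planned estimate are unaffected.

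The session numbers need no assumption beyond the schedule's own numbering. That the author meant weeks is inferred, and Fig. 1 could not be consulted. This should be corrected because it is a wrong figure in an operational instruction, although it does not threaten the primary analysis.

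**What to change.** In the Blinding section, replace the visit numbers with session numbers: session 18 (visit 21) for the mid-point, and the last stimulation session for the end. The end question then falls at session 36 (visit 39), or at visit 40 before outcome scoring if the tDCS listed there is delivered. The 36-session count and the visit 40 list must be reconciled by the sponsor. Do not tie the question to calendar weeks, given the 14-week allowance.

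Add the question to the written Visit Schedule, and report the guesses by arm at both times in a descriptive table.

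The cost is one sentence, one schedule line and one table. The two questions stay the same and no visit is added.

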improvement in working memory (41, 42); stimulation to primary motor cortex improved motor learning (43); tDCS delivered to primary motor area or to visual area V5 induced improvements in visuo-motor coordination (44); anodal stimulation of fronto-polar regions improved probabilistic classification learning (45); and left prefrontal cortical stimulation lead to increased verbal fluency. Cathodal stimulation decreases cortical excitability in humans - i.e., affected neurons will be less likely to fire (46). The above studies attest to the efficacy and safety of tDCS in stroke patients, as well as its potential for therapeutic applications in stroke recovery.

It remains to be determined if non-invasive brain stimulation could be used to further enhance the effects of behavioral training such as robotic therapy. Anodal tDCS, applied at rest over the primary motor cortex can raise corticomotor excitability and transiently improve motor function in healthy participants, and chronic stroke patients (38, 47). No reported studies of tDCS have investigated the physiological interactions of tDCS and highly controlled motor training, like robotic training, and additionally reported detailed kinematic changes. Again we are aware of the flux in this field and of the scientific details that are not currently available, but the procedures with the appropriate constraints are safe and may be clinically effective (48).

In this protocol we will test the effectiveness of adding tDCS to the standard robotic training. Despite the best efforts of current standard clinical rehabilitation, stroke survivors are left with significant and seemingly permanent motor impairments. New clinical data in the past decade supports the use of intensive re-training efforts to abet motor recovery. The rationale for intensive re-training, as in this robotic protocol, derives from experiments in pre-clinical and clinical work in which activity-dependent plasticity leads to improved motor outcome.

Specific Aims

SPECIFIC AIM 1: To evaluate whether multiple sessions of combined tDCS and robotic upper limb training in patients with chronic hemiplegia after stroke, leads to a sustained clinical improvement in upper limb motor function.

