In patients with chronic stroke (>6months post-injury, stable unilateral motor deficit) using a within-subjects repeated-measures design we will evaluate the effects of 12 weeks of robotic upper limb training (3x/week, 36 sessions, shoulder/elbow/wrist in alternating sessions) with real or sham tDCS before the robotic training. Functional improvement will be determined by a change in upper-limb Fugl-Meyer (primary), Wolf Motor Function Test, Barthel Index, and Stroke Impact Scale (secondary) outcome measures following the training, and assessed again six months later.

SPECIFIC AIM 2: To identify and compare kinematic performance characteristics between intervention groups.

Quantitative measurements obtained from robotics are highly sensitive, precise and reliable. These data will provide important contributions to understanding the components of motor control that underlie improvements in clinical function. Previously published studies and new pilot data from our group support the hypothesis that a relationship may exist for five key parameters (mean speed, peak speed, smoothness, aim, deviation) (50), however confirmation in a larger number of patients needs to be established. This information may additionally be useful as a clinical predictor of motor recovery. Since movement smoothness was shown to improve with just one session of tDCS and robotics, we predict that there will be a strong and sustained effect on this parameter. Movement smoothness is associated with more

advanced stages of motor learning, and has high correlation with functional clinical scales, and as such should be mirrored with change in Fugl-Meyer score.

SPECIFIC AIM 3: To identify and compare the neurophysiological characteristics between intervention groups.

The relationship between clinical improvement and neurophysiological measures pertaining to robotic motor training following stroke are presently not described in the literature. By measuring accepted, quantitative and reliable EMG response (wrist and elbow flexor/extensor muscles) to TMS (cortical inhibition and excitation) we will establish: (i) the plasticity associated with training, and (ii) the neurophysiological characteristics of patients (and muscles within patients) who respond to training. By understanding how brain excitability changes underpin motor dysfunction, and motor recovery, interventions can be more effectively prescribed and prognoses established.

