All outcome measures will be recorded three times prior to the training period separated by one week to ensure reliability and stability of measures, then again following the 12-week training program, and six months later. In general, study visits will take place at the institution of recruitment (e.g. subjects recruited through Feinstein will be treated at Feinstein). However, occasionally TMS and clinical assessments may take place at the other institute. Individual patient assessments will always be performed by the same evaluator to ensure internal consistency.

Fugl-Meyer (Primary): The Fugl-Meyer scale is a valid and reliable evaluation instrument used for measuring performance-based impairment in stroke patients (54, 55).

Medical Research Council motor power score (MRC): The MCR is a valid and reliable score that measures strength in isolated muscle groups of the involved shoulder and elbow on an ordinal scale (scale range: 0, no muscle contraction; 5, normal strength) .

Wolf Motor Function: The Wolf Motor Function Test is a valid and reliable assessment of upper extremity function by asking the patient to complete 15 motor-based tasks and two strength-based tasks (56).

Barthel Index (BI): The BI is a valid and reliable index of independence widely used in scoring improvement in the rehabilitation of stroke population (57). The BI consists of 10 items assigned various weightings: 15 points for the subcategories of walking and transfers; 10 points for the subcategories of feeding, bowel, bladder, toileting, dressing and stairs; 5 points for the subcategories of bathing and grooming. The BI is a cumulative score achieved by summing the score for all sections. The BI scores are recorded in multiples of 5, ranging from 0 (completely dependent) to 100 (independent in basic activities of daily living).

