Methods to address specific aim 1: We will compare demographic, clinical, kinematic, and tDCS variables between intervention groups using t-tests to compare means and chi-squared tests to compare proportions; where continuous data is non-parametric as defined by Shapiro-Wilk or Q-Q plots, we will use Kruskal Wallis tests. To assess the univariate relationship between treatment group and upper limb Fugl-Meyer score, repeated measures ANOVA will be used in order to account for longitudinal evaluations. Multivariate methods will include linear mixed models and ANCOVA to adjust for interactions or other covariates potentially contributing to the association between treatment and outcome. Further, Pearson correlation coefficients will be assessed to identify any linear association between kinematic, clinical and tDCS data points. The Spearman Rank correlation coefficient will be used for non-normally distributed variables. Like the Fugl-Meyer, secondary outcome measures, Wolf Motor Function, Barthel Index and Stroke Impact Scale are scored on a continuous scale and thus, will be analyzed as above. The MRC is scored on a scale from 0-5; Fisher analyses will be used to look for differences in strength between groups.

Specific Aim 2 (Kinematic): Determine if there is a statistically significant difference in a) mean speed, b) peak speed, c) smoothness, d) aim, and e) deviation from the straight line between subjects trained with and without tDCS prior to robotic training. This will be determined for both the trained tasks, as well as for the untrained, circle-drawing task. We will also include a static and dynamic quantitative measure of strength using the robotic device.

Methods to address specific aim 2: To assess the univariate relationship between treatment group and outcome, repeated measures ANOVA will be used in order to account for longitudinal evaluations. Multivariate methods will include linear mixed models and ANCOVA to adjust for interactions or other covariates potentially contributing to the association between treatment and outcome.

Specific Aim 3 (Neurophysiology): Determine if there is a statistically significant difference in: a) RMT, (b) MEP amplitude at 120% RMT, and c) SICI between subjects trained with and without tDCS prior to robotic training, both immediately following the training regimen, and 6 months later.

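### The primary Fugl-Meyer analysis names no deciding term or visit, no model is stated to hold the randomisation stratum, and the lead-in scores have no stated adjustment role; specifying the already listed mixed model settles this at no cost in patients

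*Combined protocol and SAP*

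**What the plan says.** Specific Aim 1 asks whether combined tDCS and robotic training "leads to a sustained clinical improvement in upper limb motor function". Improvement is judged on Fugl-Meyer (primary) and other "outcome measures following the training, and assessed again six months later". Clinical Outcome Measures gives the schedule. For the lead-in it says: "All outcome measures will be recorded three times prior to the training period separated by one week to ensure reliability and stability of measures". Two further recordings come after treatment starts: "then again following the 12-week training program, and six months later". That makes five Fugl-Meyer assessments, three before treatment and two after.

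Under Statistical Considerations, the Aim 1 test concerns a "statistically significant difference in the change in upper limb Fugl-Meyer and Wolf Motor Function score" between groups, with no visit named. The methods paragraph then says that, for the "univariate relationship between treatment group and upper limb Fugl-Meyer score, repeated measures ANOVA will be used in order to account for longitudinal evaluations". Mixed models and ANCOVA follow, for interactions or covariates that are not listed. No model is called primary. By contrast, the Aim 3 statement names both post-training times.

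The POWER paragraph is built on a twelve-week change: 2.88 with robotics alone, 4.33 with tDCS added, SD about 1.5, two-sided alpha of unstated level, 28 per group.

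On the stratum, Randomization says "we will use blocked stratified randomization to ensure our two comparison groups are balanced with respect to this known prognostic factor". No analysis paragraph mentions it again.

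**The concern.** A repeated-measures ANOVA over these visits produces several tests of treatment. The group main effect averages over visits, three of which precede treatment. The group-by-visit term is an omnibus test of any difference in profile. A group effect on change averaged over the two post-training visits is a third reading, and single-visit contrasts are further ones. They answer different questions and have very different power, and the plan does not say which decides the primary outcome. Of those listed, only the single-visit contrasts tell the reader whether a benefit at discharge is still there six months later, which is what Aim 1 asks.

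Two smaller points follow from the same paragraph. The randomisation is stratified on a factor that the plan calls prognostic; if it is, an analysis that omits it has standard errors that are too large. And three baseline scores are collected with a reliability purpose, but nothing says how they are combined or whether the model adjusts for them.

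**Working it through.** **Inputs.** From POWER: 28 per arm, difference 4.33 - 2.88 = 1.45, SD 1.5, read as the SD of a change from one baseline. Assumed: two-sided alpha 0.05, between-patient SD 8, complete data.

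**The plan's own figure.** Standard error 1.5 × √(2/28) = 0.401; 1.45/0.401 = 3.62. With 54 degrees of freedom, power is 94.4%, not the stated 90%, for which 24 per arm would do. Two-sided 0.025 gives 90.2% at 28 per arm, so the unstated alpha may explain the difference. Enrolment reproduces: 56/0.85 = 65.9, so 66.

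**Group main effect over five visits.** A sustained 1.45 averages to 2 × 1.45/5 = 0.58. A discharge-only benefit averages to 1.45/5 = 0.29. The SD of a patient's five-visit mean is about 8.01, so the standard error is 8.01 × √(2/28) = 2.14. Power is 5.8% (sustained) and 5.2% (discharge only). The result depends on the patient SD. With compound symmetry and between-visit correlation from 0.99 down to 0.5, power for a sustained benefit runs from about 5% to 45%.

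**Other tests, by simulation.** Score = patient effect + error (variance s_e²); post-training visits add a patient-specific response (variance s_r²). The two satisfy 2s_e² + s_r² = 2.25, and h = s_r²/2.25 is set to 0, 0.5 or 0.78, with the response shared by both post-training visits or independent. There were 20,000 runs per cell. With complete data the mixed-model contrasts were computed as ANCOVA at each visit on the three-baseline mean. Ranges are over the five cells, in % significant:

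| Test | No effect | Discharge only | Half left at 6 months | Sustained |
|---|---|---|---|---|
| Group-by-visit, Greenhouse-Geisser | 4.6-5.0 | 91.7-98.6 | 90.0-96.5 | 96.6-99.8 |
| Group-by-visit, uncorrected | 5.0-9.7 | 94.6-99.8 | - | - |
| Discharge contrast | 5.0-5.4 | 95.4-99.2 | 95.4-99.2 | 95.4-99.2 |
| Discharge then 6 months, both favouring tDCS | - | 2.4-2.8 | 43.4-57.4 | 91.3-98.4 |

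The discharge contrast uses only discharge data, so its power does not depend on what happens later. The 2.4-2.8% is roughly the one tail of a true null at 6 months.

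**Average of the two post-training changes.** For a discharge-only benefit the difference is 1.45/2 = 0.725, and power by noncentral t is 44.7-78.6% across the cells with one or three baselines.

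**Value of the lead-in mean.** The change from a three-score mean has variance (4/3)s_e² + s_r² = 2.25 × (2/3 + h/3). The SD is 1.22, 1.37 and 1.44 for h = 0, 0.5 and 0.78. Power is 99.2, 97.3 and 95.8%, against 94.4% from one baseline.

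**Stratum.** If the stratum explains a share R² of the variance, omitting it after stratified randomisation widens intervals by about 1/√(1 - R²). The documents give no R², so these values are illustrative (56 patients, blocks of 4, even split, simulated):

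| R² | 0 | 5% | 10% | 20% |
|---|---|---|---|---|
| Width ratio without stratum | 1.000 | 1.026 | 1.056 | 1.122 |
| Type I error without stratum, % | 5.1 | 4.5 | 3.9 | 2.7 |
| Power without / with, % | 94.3 / 94.4 | 94.7 / 95.2 | 95.2 / 96.1 | 96.2 / 97.9 |

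**The case against.** The strongest reply is that the visit is less open than it looks. Aim 1 lists the post-training assessment first, the sample size rests on a twelve-week change, and the formal Aim 1 test statement does not ask for a sustained effect. This stands in part: the text points to discharge, and the fix adopts it, but no sentence makes it decisive.

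Second, the proposed discharge test is also positive in 95-99% when benefit is at discharge only, so it is no better than the group-by-visit test at showing durability. That is correct. A reader might infer that the new primary test guards against a fading effect; it does not. Only the labelled 6-month step does.

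Third, a reader might infer that the lead-in scores are absent from every planned model. The documents do not support that. A five-visit ANOVA can hold them as repeated levels, a change outcome needs a baseline, and the ANCOVA could adjust for them. What is missing is a stated adjustment role and a rule for combining the three.

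Fourth, the unlisted covariates could include the stratum, and its stated rationale is that "stroke patients may differentially respond to non-invasive motor cortex stimulation protocols according to whether the lesion includes cortex". That describes differential response, which a main-effect term does not test; a treatment-by-stratum term would be a separate secondary analysis. The main effect is justified by the stratified design. The error from omitting it is conservative, and adjustment gains at most 1.7 points of power in the range tried.

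Fifth, the uncorrected type I error of up to 9.7% needs assumed response heterogeneity and no sphericity correction. The plan neither adopts nor rules one out.

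**Conclusion.** The point holds as a free improvement. The firmly documented part is that the primary analysis has no deciding term, no deciding visit and no stated primary model, and that the stratum is in no named model. The consequence is not that the trial is underpowered. That inference would follow only if the group main effect were the test, and the plan's language of change makes other readings at least as likely. The consequence is that the available readings range from about 6% to nearly 100% power for the same sustained benefit, and that the well-powered omnibus test does not say whether benefit lasts.

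The gain from the fix is a separate 6-month contrast, with false claims of sustained benefit in about 2-3% when benefit is at discharge only. There is no power gain over the group-by-visit test. Against a change from one baseline, power rises from 94.4% to 95.8-99.2%.

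These figures rest on alpha 0.05, SD 1.5 as a change SD, patient SD 8 for the main effect, and complete data. Behaviour under the planned 15% attrition was not examined. The stratum figures are illustrative.

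**What to change.** Make the linear mixed model that is already listed the primary analysis, in all randomised patients with available data:

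- Outcomes: Fugl-Meyer at discharge and at 6 months.
- Terms: treatment, visit, treatment-by-visit, mean of the three lead-in scores, cortical/subcortical stratum; unstructured covariance.
- Step 1: the treatment difference at discharge decides the primary outcome.
- Step 2: test the 6-month difference only if step 1 is significant, and claim sustained benefit only if both are significant in favour of tDCS. Report the 6-month interval in any case, because a non-significant result there does not prove that benefit has faded.

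The sponsor should confirm discharge as the deciding visit, state the alpha level, and say openly that step 1 alone says nothing about durability. The fixed order keeps type I error at 5% for Fugl-Meyer only; Wolf Motor Function, named beside it in the Aim 1 test statement, is not covered. If the repeated-measures ANOVA is kept as supportive, name the group-by-visit term and apply Greenhouse-Geisser.

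The cost is wording, provided that it is settled before the allocation code is revealed. The scores and the stratum are already planned, so no patient, visit or measurement is added. The two adjustment terms use 2 degrees of freedom, with no measurable loss of power if the stratum explains nothing.
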